Table 3. Summary of Mind-STRIDE Participant Feedback: Themes and Supporting Veteran Quotes from Satisfaction Questionnaires and Home Practice Journals

Mindfulness as a personal resource

- “Provides another tool to help keep you on track.”
- “Helps make things easier.”
- “It definitely helps me feel better, a great tool.”
- “It got me through a really tough day when my wife was sick and my car broke down. Extension of principles from anger management to practical use in diabetes program for control.”
- “This presentation/study is very useful and I would strongly suggest this type of study to Veterans that I counsel (unemployed Veterans).”
- “I find it very helpful as it helps you to concentrate on things that will help you to feel better about yourself.”
- “This should help some people if they are willing to commit to doing this.”
- “Good way to help people understand their bodies.”
- “More classes. Very helpful - interesting. Need more involvement.”

Awareness

- “This helped become more aware.”
- “This class is showing me a different approach in dealing with my thinking!”
- “I was surprised how much I did not hear until I took this class. Just never paid attention to surroundings... took most things for granted...”
- “This program has given me the thought about what is meaningful in life! Stress relief is certainly important and attainable! Thinking about everyday thoughts and feelings are important!”
- “Good way to help people understand their bodies.”
- “Class was good and made me consider my thought processes.”

Home Practice

- “Interruptions during my home study disrupted the thoughts I was having.”
- “I have problems with attention deficit at home. My mind wanders even though I try to stay focused.”
- “It helps when you do it on a continuing daily basis; I found different times of day work best.”
- “Mindfulness recordings are very helpful.”

Social support

- “I was skeptical but my wife said ‘Give it a try. I’m glad I did.’”
- “My wife and I have been doing it together.”
- “I think it was good talking with other diabetics about what they think and feel, that I am not the only one with these feelings.”

Behavior change

- “My wife asked me why this motivates me... after all this time.”
- “Curious to continue this process and see my personal experiences and results!”
- “I’m sticking with it, because I want to help myself do better.”

Nonparametric repeated measures analysis and post-hoc pairwise comparisons were applied to the quantitative data using the Friedman's Test and Wilcoxon Signed Rank Test respectively and demonstrated a statistically significant reduction in DRD from baseline to 3-months post intervention ($p < .01$; $d = .7$). Significant improvements in diabetes self-management ($p < .05$; $d = .5$), and a 1% reduction in HbA1c ($p < .05$; $d = .7$) were also observed. After 3-months of mindfulness practice, significant correlations were found between psychological outcomes and specific elements of Mindfulness that were not present at baseline (Table 4).

Table 4. Post-intervention Correlations between Mindfulness Facets and Psychological Outcomes

Mindfulness (FFMQ)	Perceived Stress (PSS-10)	Diabetes Distress (PAID)	Diabetes Self-Efficacy (DES-SF)
Observing	-.05	-.04	.11
Describing	-.18	-.12	.50*
Acting with awareness	-.59**	-.54**	.42*
Non-judgment	-.59**	-.53**	.43*
Non-reactivity	-.30	-.52**	-.04

* $p < .05$; ** $p < .01$

Implications for the proposed study. We pilot-tested the feasibility of operationalizing Mind-STRIDE within existing DSME classes. Rates of recruitment and retention were generally good, Veteran satisfaction and engagement and staff satisfaction and enthusiasm were high. However, only 39% of participants completed diaries, therefore we concluded that the use of paper home practice diaries was inefficient for tracking home practice. We believe hand-held digital devices will be easier and more appealing to the participants and therefore will increase participation in this exercise. These devices can be used for more portable and convenient access to the audio-recorded guided meditations and for real-time documentation of home meditation practice; and they can also serve as a home practice journal. This pilot study paved the way for taking the next step, testing the effects of the intervention on glycemic control and intermediary psycho-behavioral outcomes in the proposed RCT.

2.0 Significance

One in four US veterans who receive care through the VHA have diabetes, which means that at any given time more than one million Veterans look to the VHA for diabetes care and self-management support.¹

Management of diabetes depends upon self-management behaviors to regulate metabolic control and prevent or delay micro-vascular and macro-vascular complications. Advanced micro-vascular complications of diabetes are the leading causes of blindness, non-traumatic amputations, and end-stage kidney disease in the US and in VHA. VHA patients have a higher rate of diabetes (11% vs. 8%) compared to the general US population. Advanced macro-vascular complications such as myocardial infarction and stroke contribute to higher mortality rates in VA patients with diabetes, which average 5% compared to 2.6% among patients without diabetes, and is a major cause of deaths and inpatient admissions outside of VHA¹. Diabetes is one of the top medical conditions requiring hospital admissions and 30-day readmissions, and therefore is a significant contributor to escalating health care costs.⁶⁵

The anticipated impact of this study is to decrease DRD and enhance self-efficacy to improve diabetes self-care behaviors through mindfulness and potentially improve glycemic control among Veterans. Because DRD interferes with self-care behaviors, our program has potential for significantly impacting and advancing the health and health care of Veterans because it targets a serious and prevalent problem that is not currently well-addressed within the context of diabetes care. The proposed mindfulness study will extend knowledge of the feasibility and effects of providing a practical, low cost, mind-body intervention that can be offered as a part of routine DSME, and has already been successfully pilot-tested in a sample of Veterans who found it acceptable and helpful. This is not surprising in that approximately 21 million US adults, including Veterans, practice mindfulness or some form of meditation.⁶⁶ Mindfulness is increasingly incorporated into Complementary CAM initiatives in VHA. Mindfulness is one of the top five most frequently used mind-body CAM modalities at VA facilities. Studies of mindfulness meditation in Veterans with PTSD have shown improvements in PTSD symptoms and improvements in quality of life.^{47, 67} Over 5,000 Veterans have been treated with mindfulness meditation at VA facilities for anxiety, PTSD, depression and stress management.⁶⁸ Over half of VHA facilities have existing procedures for mindfulness in place and offer mindfulness therapy primarily to Veterans

receiving outpatient care. However, mindfulness meditation has not been studied or applied to the care of patients with diabetes within VHA.

The proposed study supports VHA National Nursing Strategic Plan (2013-18) goal 1a(4) by testing the integration of a new nurse-led initiative into a patient-centered program of specialty care. This proposal also corresponds with VHA Blueprint for Excellence (9-2014) transformational action 7.2 by testing a program that will enhance VA Research on CAM. Empowering Veterans to improve their own wellbeing is one of the driving strategies behind VA CAM research. VHA has funded 13 mind-body studies in partnership with the National Center for Complementary and Alternative Medicine that target pain and PTSD in active duty personnel and in Veterans and their families. However, currently, there are no planned VA studies of mindfulness-based therapies for diabetes.

Considering the cumulative effects of stress and the number of military Veterans who suffer from co-morbid depression and PTSD,^{57, 69} Veterans with diabetes are at particular risk for negative consequences of diabetes distress. Mind-STRIDE re-directs the current intervention paradigm for DSME and diabetes care, and could pay-off with a ready-to-use program choice for Veterans that offers effective psycho-behavioral self-management support through patient-aligned care. Considering that our Co-Investigators are prominent VA, national, and international leaders, [name] and [name] in the field of diabetes care and education, and [name] and [name] in meditation and mindfulness, the likelihood of uptake of findings and recommendations from the proposed research is high. Mind-STRIDE has minimal potential for harm, and holds promise for enhancing the physical and psychological health of Veterans to better equip them to *“manage their own lives and achieve their own goals.”*⁷¹ We also anticipate that in the future, programs similar to Mind-STRIDE might have applicability for supporting Veterans’ self-management goals in prevention and maintenance of other chronic conditions. In fact, this study is closely aligned with currently and previously NRI- funded mindfulness and meditation trials for PTSD⁶⁷ and cardiovascular risk in women (The Mindful Hearts Trial). Together these nurse-led studies will build upon one another to make substantial contributions to the emerging literature and science of mindfulness and meditation in Veterans who are at risk for and suffer from chronic diseases.

2.1 Innovation

Our intervention is noteworthy and novel in four ways:

- a) **Content:** Mind-STRIDE is an original VA pilot-tested intervention adapted from an evidence-based Mindfulness training model, MBSR
- b) **Accessibility:** Our program incorporates a brief, accessible mindfulness-based intervention provided at the point of diabetes care, and tests the efficacy of a potentially new diabetes care process geared toward uptake and sustainability
- c) **Design:** Our study is the first to apply a qualitative analysis of mindfulness in people who have diabetes, which actively supports the design and implementation of a new patient-centered diabetes paradigm
- d) **Measurement:** Our study is the first to utilize common technology (digital tablets) to capture adherence to home mindfulness practice in real time, as well as utilize existing VA Tele-Health technology for verification of home blood glucose data

3.0 RESEARCH DESIGN AND METHODS

3.1. Design

This study is a 2-arm single-site mixed-methods randomized controlled efficacy trial of a mindfulness intervention to reduce DRD among Veterans with diabetes. Participants will be randomized to one of two study conditions: the experimental group (DSME+ Mind-STRIDE) and the usual care group (DSME-Alone). Research assessments will occur at baseline (T1), 12- weeks (T2), and at 24 weeks (T3) for both study arms. Satisfaction assessments will be conducted in the experimental group following the Week 4 booster. Qualitative telephone interviews will be conducted at 15 weeks in a subgroup of purposively sampled participants in the experimental group.

3.2 Setting

This study will be conducted at the University Drive (UD) campus of VA Pittsburgh Healthcare System (VAPHS), an integrated healthcare system affiliated with the University of Pittsburgh that serves the Veteran population throughout the tri-state area of Pennsylvania, Ohio, and West Virginia. VAPHS is a major tertiary care institution comprised of two facilities and is the hub to five smaller “spoke” facilities in the region; it provides specialty diabetes care to five regional Community-Based Outpatient Clinics (CBOCs), for which it provides diabetes specialty care services. VAPHS provides outpatient health care to approximately 17,000 US Veterans with diabetes annually, 28% of the total number of patients served. The UD location is the only VA location in the tri-state area of Southwestern Pennsylvania, Southeastern Ohio and Northern West Virginia that has a Diabetes Specialty clinic and offers group DSME classes (Additional information about VAPHS is found in the *Facilities and Resources* section.) The Diabetes Clinic is housed within the multi-disciplinary Medical clinic in the hospital facility at UD, and is staffed by four board certified endocrinologists, two nurse practitioners (one is the PI), three certified diabetes nurse educators, and a dietitian. The staff diabetes educators and dietitian provide individual diabetes education in the outpatient clinic by appointment in addition to teaching the comprehensive group DSME classes. Group classes are held twice monthly throughout the year in a conference room at UD and are offered twice monthly via direct video-conferencing from UD to Veterans gathered at spoke facilities. The coordinating diabetes nurse educator co-teaches the DSME class with the dietitian and received over 300 DSME referrals from primary care and specialty clinic providers at UD and 160 referrals from spoke facility providers in 2014. The VA DSME program meets national standards and maintains recognition by the America Diabetes Association (ADA) Education Recognition Program (ERP).²⁴

3.3 Population and Sample

The target population for this study is male and female Veterans who have a diagnosis of T1DM or T2DM. We will use the following inclusion and exclusion criteria for our study sample:

Criteria for inclusion:

- a) DSME class enrollment*
- b) Fluency in reading and writing English**
- c) Diagnosis of diabetes for at least 6 months *
- d) HbA1c >7.5% within past 3 months *
- e) Stable diabetes medications for at least 60 days*
- f) Problem Areas in Diabetes Scale (PAID) score > 10 (described below, Section 3.8)**
- g) Telephone access with voice mail to receive research related messages**
- h) Willingness to utilize VA Home Tele-Health for documentation of home blood glucose readings**
- i) Willingness to be randomized to the experimental or usual care group**
- j) Willingness to have the qualitative interview audio-recorded (if randomized to experimental group)**

Criteria for exclusion:

- a) Active meditation practice **
- b) Documented cognitive impairment including active psychosis, dementia or other organic mental disorders, that may interfere with the ability to comprehend the informed consent and/or actively participate in the study*
- c) Previous attendance of VA DSME class within the past 12 months *
- d) Planned relocation from the Pittsburgh area within the next 6 months**

*Determined by pre-screening of VA computerized Patient Record System (CPRS)

**Determined by telephone screening interview

3.4 Procedures

An overview of the study design and procedures appears in Figure 3. All participants enrolled in DSME will be pre-screened by the Research Assistant, pursuant to IRB approved HIPPA Waiver, for inclusion and exclusion criteria. Prior to the DSME class, the staff diabetes educator will contact eligible candidates to obtain assent. The Research Assistant or Research Coordinator will then contact assenting participants for telephone screening for additional inclusion/exclusion criteria pursuant to an IRB approved Waiver of Documentation of

Informed Consent for Screening. After informed consent procedures are completed, enrolled participants will complete Baseline (T1) pencil-and paper research assessments administered in-person by the Research Assistant. After completion of T1 assessments, participants will be randomly assigned to either the experimental condition (DSME+ Mind-STRIDE) or the usual care condition (DSME -Alone) (See Randomization Procedure). Subsequent post-intervention research assessments will be completed at week 12 (T2) and week 24 (T3), and will consist of biological measures (height, weight, blood pressure, and laboratory assessment of HbA1c) performed by clinical staff, and completion of paper and pencil assessments administered in person by the Research Assistant or Research Coordinator. In the DSME + Mind-STRIDE group, participants will also complete the participant satisfaction assessment administered by the Interventionist following the 4-week booster. A purposively sampled subset of 25-participants will complete a qualitative telephone interview at 15-weeks (between T2 and T3).

Participants in both groups will attend the 4-week DSME follow-up booster visit with the staff dietitian who is not part of the study team. The study interventionist will deliver the Mind-STRIDE booster to participants in the experimental group immediately following that dietitian visit. The Interventionist will administer the satisfaction questionnaire to Mind-STRIDE participants after completion of the booster session, and will ensure confidentiality by asking participants to seal completed surveys in provided envelopes. In addition, all participants will receive a monthly post-card from the study team to help promote engagement and retention in the study. All participants will receive reimbursement for participation in the study following each assessment (\$50 at T1, \$75 at T2, and \$100 at T3) and will also receive a digital tablet as remuneration for their participation. DSME + Mind-STRIDE participants will receive the tablet following the initial Mind-STRIDE intervention; DSME–Alone participants receive the tablet following completion of T3.

Figure 3. Study Design and Procedures

[figure not shown]

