1.7 Relevant Research—Preliminary Studies

We have conducted two surveys and two pilot studies in preparation for the current RCT proposal that demonstrate Veteran preference for accessible and personalized interventions, as well as Mind-STRIDE's feasible and outcome-driven approach that warrants efficacy testing.

1.7.1 MBSR for United States (US) Military Veterans with Diabetes: A Survey of Interest among Veterans (PI: [name], RN)

The purpose of this descriptive study was to determine Veteran interest in learning more about stress management and participating in an 8-week MBSR program at VAPHS. We conducted a survey of 51 US Veterans with T2DM from December 2008 to March 2009 at the VAPHS Diabetes Clinic. Respondents were mainly white (84%), men (98%), 55 years of age or older (78%). Of those polled, 31 Veterans (61%) reported having an interest in attending the MBSR program. Sixty-one percent requested printed information on stress management; 78% identified the MBSR program's location as being a decisive factor to their willingness to participate in a multiple-session study. These 61% of interested respondents identified wanting to attend the program for the following reasons: for general stress reduction (48%); to improve diabetes control (23%), to manage weight and overall health (20%), to improve self-esteem (3%); and/or to learn something new (6%). Twenty respondents (39%) had no interest in attending the proposed MBSR program; reasons for no interest included: lack of transportation/unable to commit to eight weekly sessions (40%); having no stress or stress under control (45%) or no interest in this type of program (15%). These findings were presented in a poster presentation at the 2009 Eastern Nursing Research Society (ENRS) conference in Providence, RI.

Implications for the proposed study. From this survey we gained a sense of the demographic characteristics and interests of patients who receive care at VAPHS Diabetes Specialty clinic. Although their degree of interest in attending a stress management program at VAPHS was high, we concluded that recruitment for a multi-session face to face program at VAPHS would be difficult, since the travel and time commitment was a barrier for many of the Veterans who were surveyed.

1.7.2 Stress Reduction in Diabetes Education: A Survey of Interest among Diabetes Educators (PI: [name], RN)

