3.7 Data Analysis

3.7.1 General Analytic Approach for Aim 1:

Aim 1: To compare the effects of the intervention (DSME+ Mind-STRIDE) with those of usual care (DSME-alone) on diabetes distress, diabetes self-efficacy, and DSM in military Veterans over time.

Hypotheses. From baseline to 24-week post-intervention, DSME+ Mind-STRIDE compared to DSME-Alone will:

1. Significantly reduce DRD (primary outcome)
2. Significantly increase mindfulness, diabetes self-efficacy and diabetes self-management (secondary behavioral outcomes)
3. Significantly decrease HbA1c (distal metabolic outcome)

Independent variable: The Mind-STRIDE intervention, which includes mindfulness stress reduction, mindfulness meditation training and home practice.

Dependent variables: The primary outcome on which the analysis is powered is DRD measured by the PAID scale. Secondary outcomes include diabetes self-efficacy, diabetes self-management, mindfulness, and glycemic control, measured by HbA1c.

Analysis: To assess whether there are group differences over time, we will use separate linear (or non-linear depending on outcome) mixed models for each outcome (diabetes distress, primary), diabetes self-efficacy, diabetes self-management, mindfulness and glycemic control (secondary) for 3 time points (baseline, 12 weeks post-intervention, and 24 weeks post-intervention). The base model will include fixed effects for treatment group DSME+ Mind-STRIDE, DSME-Alone group, time, and the interaction between treatment group and time. To the extent possible, post-hoc analyses to explore the possible relationships between mindfulness and diabetes-related distress (as well as the interaction between them) on the distal secondary outcome, glycemic control will be performed.

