Power analysis: Power calculations for Aim 1, hypothesis 1 of this study were based on a repeated measures design (2 sided $\alpha = .05$) with 2 treatment groups (DSME+ Mind-STRIDE; DSME-Alone) and 3 time points (baseline, 12 weeks post intervention, 24 weeks post-intervention). We computed sample size estimates that were powered to detect an overall treatment group difference in DRD (PAID scale score) as well as a treatment group difference over time (interaction between treatment group and time). Based on our pilot work, a medium effect size ($d = .6$) gives a clinically meaningful change in PAID score. Using a medium ($d = .5$) effect size, and estimates of the correlations between observations on the same subject of $r = .5$, powering at 80% gives a sample size estimate of 86 (~43 per group). To account for possible clustering due to the randomization occurring in groups of $n = 5$ participants, the required total sample size (86) was inflated by a factor of $(1 + (5-1) * p)$, where p is the intra-cluster correlation coefficient.^{78, 79} A conservative estimate of the intra-cluster correlation of $p = 0.05$, gives an increased sample size of 104 (~52 per group). To ensure a sample of 104 at study completion, 126 Veterans will need to be recruited over the 2-year study period. This number of 126 Veterans is approximately 20% of the usual number of Veterans referred for DSME over two years and is within what is considered reasonable to recruit based on our pilot data. Sample size estimates were computed in Stata Statistical Software: Release 12 (College Station, TX: StataCorp LP; 2011).

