[name] PhD, Associate Professor of Biostatistics at the University of Pittsburgh Graduate School of Public Health, will oversee statistical analysis for Aim 1. Analyses for Aim 1 will be performed using Stata statistical software. Diabetes distress (the primary outcome) and secondary outcomes (mindfulness diabetes self-efficacy, diabetes self-management, and HbA1c) will be assessed for normality and appropriate data transformations will be used if necessary. Descriptive statistics will be computed to determine central tendency, data sparseness, and existence of outliers for all other continuous variables. Frequency distributions will be generated for categorical variables to identify data sparseness, and categories with small frequencies will be merged when appropriate. In addition, we will consider categorization of continuous predictors if the distributions are skewed or violate assumptions of linearity. Differences in covariates by treatment group will be tested using chi-square (or Fisher's exact) statistics for categorical variables and t-test (or Mann-Whitney) for continuous variables. Graphical procedures will be used to assess simple change in the outcomes over time. For the main analyses for Aim 1, we will test study hypotheses by using linear mixed models (or non-linear

mixed models where appropriate), which account for repeated measures and assess change over time (baseline, 12 weeks, 24 weeks). The linear mixed model allows for missing data if data are missing at random. Demographic variables with a univariate association with the outcome ($p < 0.10$) or differed by treatment group at baseline ($p < 0.05$) will be considered for inclusion in a multivariate model. Covariates will be retained in the final multivariable models if significant at $p < 0.05$. All tests will be two-sided. All analyses will be conducted as intent-to-treat analyses and include all patients in the groups to which they were randomized, regardless of adherence and/or subsequent withdrawal.

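### PAID at weeks 12 and 24 has only an in-person route, so Veterans who attend neither visit drop out of an analysis promised as intent-to-treat

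*Combined protocol and SAP*

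**What the plan says.** Section 3.7.1 makes every analysis intent-to-treat. It will "include all patients in the groups to which they were randomized, regardless of adherence and/or subsequent withdrawal".

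Section 3.4 describes the T2 and T3 visits as biological measures taken by clinical staff plus "completion of paper and pencil assessments administered in person by the Research Assistant or Research Coordinator". The visible text gives no telephone, mail or make-up route for PAID at these visits and no visit window. It also does not say that a Veteran who stops the intervention continues to be assessed.

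On timing, sections 3.1 and 3.4 and Table 5 speak of week 12 and week 24, while section 3.7.1 models "3 time points (baseline, 12 weeks post-intervention, and 24 weeks post-intervention". Randomisation follows the T1 assessments. The date from which the weeks are counted is not stated.

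Several provisions bear on loss to follow-up:
- Section 3.7.1 inflates 104 completers to 126 recruits.
- Section 3.4 provides monthly postcards and payments that rise from T1 to T3.
- The missing-data paragraph of 3.7.1 uses all available data in the mixed model, adjusts for baseline variables that differ between those with and without complete outcome data, and adds a completers-only comparison.

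PAID is already obtained without a visit. Table 5 shows it at screening, week 12 and week 24 but not at T1. In section 3.3 the PAID entry criterion carries the mark "Determined by telephone screening interview".

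**The concern.** An intent-to-treat analysis needs outcome data from the people it claims to include. If the only route to the primary outcome is a visit, those who stop coming are in the analysis set in name only. A participant with a baseline value alone adds nothing on change. The mixed model in effect assigns that person the course of others in the same arm who did attend.

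That is harmless if loss depends only on observed data. The plan itself gives reason for doubt: section 1.1 links diabetes distress, the primary outcome, to reduced adherence. Retention pressures also differ by arm. Section 3.6.3 puts the burden at about 30 hours in the Mind-STRIDE arm and 5 hours in usual care. Section 3.4 gives the tablet after the first session in one arm and after T3 in the other. Section 1.7.1 reports that "the travel and time commitment was a barrier for many of the Veterans who were surveyed".

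At stake is whether the reported effect describes all randomised Veterans or mainly those who kept attending.

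**Working it through.** **1. The plan's own figures.** Inputs from section 3.7.1: two-sided alpha 0.05, two arms, three time points, "Using a medium ($d = .5$) effect size", within-subject correlation 0.5, power 80%, groups of 5, intra-cluster correlation 0.05.

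- Base size: between-group repeated-measures F test with f = d/2 = 0.25 and noncentrality f² × N × 3 / (1 + 2r). At N = 86 this is 0.0625 × 86 × 3 / 2 = 8.06, and power is 0.801. The smallest even N reaching 80% is 86, as stated.
- Clustering: 86 × (1 + 4 × 0.05) = 103.2, or 104 in equal arms, as stated.
- Loss: 1 − 104/126 = 22/126 = 17.5%. The plan does not state the rate; this is what 126 implies.

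**2. Power under other loss rates.** The rates are assumptions, with N = 126 and design effect 1.2.

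| Loss | Evaluable | Power |
|---|---|---|
| 10% | 113 | 0.84 |
| 17.5% | 104 | 0.80 |
| 25% | 94–95 | 0.77 |
| 30% | 88 | 0.74 |

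Moderate loss beyond the allowance costs some power but is not ruinous. The allowance does nothing about bias.

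**3. Size of a possible bias.** Assumptions: 22 of 126 have no post-baseline PAID, split equally between arms; the effect in the 104 observed is 0.5 SD; those lost differ from those observed only in the share k of the effect that they keep; and baseline PAID does not predict loss. The available-data estimate is then 0.5, and the intent-to-treat effect is (0.5 × 104 + k × 0.5 × 22) / 126.

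| Share kept, k | Intent-to-treat effect | Overstatement by available data |
|---|---|---|
| 1 | (52 + 11)/126 = 0.500 | 0% |
| 0.5 | (52 + 5.5)/126 = 0.456 | 0.5/0.456 = 1.10, about 10% |
| 0 | 52/126 = 0.413 | 0.5/0.413 = 1.21, about 21% |

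**4. What a remote PAID could recover.** Suppose, as a further assumption, that it reaches half of the 22, so that 115 are observed.

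- k = 0: observed effect 52/115 = 0.452, and 0.452/0.413 = 1.10. The overstatement falls from about 21% to about 10%.
- k = 0.5: observed effect (52 + 2.75)/115 = 0.476, and 0.476/0.456 = 1.04. It falls from about 10% to about 4%.
- In either case the standard error is multiplied by √(104/115) = 0.951, about 5% smaller.

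**The case against.** The plan does not ignore loss. It recruits for it, pays $75 and $100 for T2 and T3, sends postcards, and fits a model that uses partial follow-up. The two main sessions are a 1-hour class and a 30-minute booster at week 4, so a Veteran lost at week 12 may have had both and may keep much of any benefit. Telephone PAID in a trial where participants know their arm could add a mode effect that differs by arm. Figure 3 is not shown and a procedure manual is planned, so a follow-up rule may exist elsewhere.

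These points stand as limits on the size of the problem. None of them supplies a route to PAID for a Veteran who attends neither visit. The completers-only comparison does not test for loss related to unobserved distress, because it also rests on those who attended.

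Three stronger readings are tempting, and the documents do not support them:

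- **Veterans who skip the class give no outcome.** Nothing visible makes class attendance a condition for T2 or T3. Section 3.1 sets these assessments for both arms, as research visits separate from the class and booster.
- **Usual-care participants have no intervention from which to count weeks.** Both arms attend the DSME class and the 4-week dietitian booster, so a common anchor exists. It is simply not named.
- **Travel is the main barrier in this population.** The survey in section 1.7.1 asked about an eight-week programme. Among the 20 Veterans not interested, 45% cited no stress or stress under control; 40% cited transport or inability to commit to eight weekly sessions, pooled together.

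**Conclusion.** The point holds in a limited form. The promise to include everyone as randomised is not matched by a means of obtaining the primary outcome from those who will not attend in person. The possible overstatement runs from 0% to about 21% across the assumptions in step 3, with about 10% at the midpoint. The 21% figure should not be read as an estimate, since it requires that all 22 have no follow-up PAID and that none of them keeps any benefit. If some attend one visit, or if loss is unrelated to later distress given the observed data, the bias is smaller or absent. If loss also differs between arms, or those lost differ in prognosis, it could fall outside this range.

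The missing start date and the missing statement on withdrawal are, taken alone, matters of clarification. The substantive improvement is the remote fallback for PAID.

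**What to change.** In section 3.4, add that if a participant will not attend T2 or T3 in person and has not withdrawn consent to follow-up, PAID is collected by telephone or mail: PAID first, then the other scales as feasible. Record the mode for every PAID score, and report the primary result with and without the remote values.

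In the same edit:
- Count weeks 12 and 24 from one date common to both arms, either randomisation or the scheduled DSME class date, and use the same wording in 3.7.1.
- State that stopping Mind-STRIDE or home practice is not withdrawal from assessment.

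Taking HbA1c from a VAPHS laboratory result in the patient record within a fixed window is optional and concerns only a secondary outcome.

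The cost is protocol wording and some research-assistant telephone time. Telephone access is already an entry criterion, and telephone interviews are already planned at week 15. The downside is a possible mode effect in a minority of scores. It is tempered because the entry PAID is itself a telephone score according to section 3.3 and Table 5, and it can be examined through the recorded mode. The change reduces the loss but does not end it, since some Veterans will decline the telephone as well.
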